#### 5.3 Inclusion of Women, Minorities and Children

Both men and women and members of all races and ethnic groups are eligible for this study. Children are not eligible for this study because the safety and tolerability of the proposed dosing schedule has not been determined in adults.

#### 5.4 Withdrawal Criteria

Subjects are free to discontinue treatment or withdraw from the study at any time and for any reason, without penalty to their continuing medical care. Any discontinuation of treatment or withdrawal from the study must be fully documented in the eCRF and should be followed up by the Investigator. The Investigator may withdraw a patient at any time if this is considered to be in the patient's best interest.

#### 5.4.1 Study Treatment Discontinuation

Study treatment must be discontinued if:

- There is evidence of disease progression. Subjects who have PD but who are continuing to derive clinical benefit in the opinion of the investigator may continue to receive study treatment.
- A subject becomes pregnant.
- A subject is significantly non-compliant with the requirements of the protocol.
- A subject has an adverse experience that would, in the investigator's judgment, make continued participation in the study an unacceptable risk.
- The subject starts new treatment for their underlying disease.

#### 5.4.2 Study Discontinuation

Subject is discontinued from the study if:

- The subject dies during the study.
- The subject is lost to follow-up.
- The subject withdraws consent.

# 5.4.3 Withdrawn Subjects

When a subject is removed from the study treatment, the investigator will clearly document the reason in the medical record and complete the appropriate eCRF page describing the reason for discontinuation. In addition, every effort should be made to complete the appropriate assessments listed in Section 7.3.

### 5.5 Noncompliance

All instances of protocol deviations will be recorded according to guidelines per Sponsor's Representative.

#### 6.0 TREATMENT OF SUBJECTS

#### 6.1 Drug Preparation and Administration

Study treatment may be administered on an outpatient basis. No investigational or commercial agents or therapies other than those described below may be administered with the intent to treat the subject's disease.

#### APR-246

APR-246 is administered as a 6-hour IV infusion daily on Days 1–4 of each 21-day cycle. APR-246 fixed dose is 4.5 g. APR-246 is administered in a 2-step infusion:

- Step 1: Loading dose of 1.5 g for the first 45 minutes (± 2 min)
- Step 2: Maintenance dose of 3 g over 5 hours 15 minutes (± 30 min)

The dose of APR-246 may be reduced (please consult Section 4.1 and Table 1) or treatment interrupted if the subject develops AEs.

APR-246 vials are to be stored at 2 – 8°C (35.6 – 46.4°F). At the pharmacies and at the study centers, the prepared APR-246 study product (diluted in sodium chloride solution) is to be stored at no greater than 25°C. The infusion should be completed within 24 hours from the time of preparation.

Detailed instructions on vial concentration, preparation and dispensing can be found in the Pharmacy Binder. The infusion timing, including start/stop times and the time of rate change, must be recorded.

# Pembrolizumab

Pembrolizumab at a dose of 200 mg is to be administered on Day 3  $\pm$ 1 day of each cycle before the Day 3 dose of APR-246.

# 6.1.1 Dose-Limiting Toxicity

A DLT is defined as any of the following:

- Any of the hematological or nonhematological toxicities noted in the table below considered to be at least possibly related to APR-246 occurring during the 3-week safety assessment period after the start of APR 246 administration in combination with pembrolizumab (Cycle 1 Day 1).
- Failure to administer ≥75% of the planned dosage of APR-246 as a result of treatment-related toxicity during Cycle 1, unless reversible CNS-related effects previously described for APR-246.
- Subjects who discontinue treatment due to treatment-related toxicity.
- Greater than 4-week delay in starting Cycle 2 because of a treatment-related toxicity, even if the toxicity does not meet DLT criteria.

Dose-Limiting Toxicities	5 · · · · · · · · · · · · · · · · · · ·
Toxicity Category	Toxicity CTCAE Grade
Hematologic	Grade 4 neutropenia for ≥ 7 days
	Grade 3 or Grade 4 febrile neutropenia a
	Thrombocytopenia <25,000/mm  associated with bleeding and/or that
	requires platelet transfusion
Other nonhematologic	Any other Grade 4 or a Grade 5 toxicity
toxicity	Grade 3 toxicities lasting > 3 days excluding:
	Nausea, vomiting, fatigue and diarrhea controlled by medical
	intervention within 72 hours.
	Grade 3 rash in the absence of desquamation, no mucosal involvement,
	does not require steroids, and resolves to Grade 1 by the next
	scheduled dose of pembrolizumab.
	Grade 3 hypertension not able to be controlled by medication
	Grade 3 or above gastrointestinal perforation
	Grade 3 or above wound dehiscence requiring medical or surgical
	intervention
	Any grade thromboembolic event
	Any Grade 3 non-hematologic laboratory value if: Medical intervention is
	required to treat the subject, or the abnormality leads to hospitalization
ANC = absolute neutrophil cour	nt, CTCAE = Common Terminology Criteria for Adverse Events v5.0.
a Febrile neutropenia Grade 3 o	
	00/mm  with a single temperature of >38.3 °C (101 °F) or a sustained temperature of ≥ 38 °C
(100.4 °F) for more than one ho Grade 4 is defined as ANC < $100$	ur. )0/mm³ with a single temperature of >38.3 °C (101 °F) or a sustained temperature of ≥ 38 °C
	ur, with life-threatening consequences and urgent intervention indicated

Only toxicities with a clear alternative explanation (e.g., due to disease progression) or transient ( $\leq$  72 hours) abnormal laboratory values without associated clinically significant signs or symptoms based on investigator determination can be deemed a non-DLT.

All subjects enrolled in the safety lead-in portion will be assessed for DLTs during the 3-week DLT assessment period of Cycle 1. Subjects who discontinue study treatment prior to completing Cycle 1 of study treatment for any reason other than DLT will be replaced.

Additionally, AEs that meet the above criteria, but occur after the DLT evaluation period will not be defined as DLTs, but will be reported as AEs/SAEs and will be reviewed across all cohorts during the study to help determine the AE profile.

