Objectives	
 
To evaluate the safety and tolerability of APR-246 in combination with pembrolizumab in subjects with solid tumors.
 
To determine and confirm the maximum tolerated dose (MTD) for APR-246 in combination with 200 mg IV, every 3 weeks (Q3W) pembrolizumab in subjects with solid tumor malignancies.
 

	
 
Secondary objectives:         
 
Overall response rate (ORR) (Complete Response [CR] + Partial Response [PR]) of APR-246 in combination with pembrolizumab in subjects with solid tumor malignancies by Response Evaluation Criteria in Solid Tumors (RECIST) 1.1.
 
Progression-free survival (PFS) by RECIST 1.1.
 
Overall survival (OS).
 
Duration of response (DOR) by RECIST 1.1.
 
Disease control rate (DCR: CR + PR + stable disease [SD]) by RECIST 1.1
 
Durable SD rate (durable SD [SD ≥23 weeks]) by RECIST 1.1.
 
Clinical benefit rate (CBR: CR, PR + durable SD) by RECIST 1.1.
 
 
 
The pharmacokinetic (PK) profile of APR-246 during combination treatment with pembrolizumab.
 

	Exploratory objectives:
	1. To investigate the relationship between candidate efficacy biomarkers and anti- tumor activity of APR-246 in combination with pembrolizumab based on analyses of blood, serum, and/or tumor tissue.
Study	Primary endpoints:
Endpoints	
 
Occurrence of DLTs, classified and graded according to the National Cancer Institute's Common Terminology Criteria for Adverse Events (NCI-CTCAE, version 5.0).
 

 
Frequency of treatment-emergent adverse events (TEAEs), and serious adverse events (SAEs) related to APR-246 in combination with pembrolizumab.
 
RP2D of APR-246, defined as the dose of APR-246 at which < 2 out of 6 subjects experience DLT during the 3-week safety assessment period after the start of APR-246 administration in combination with pembrolizumab using dose de-escalation of APR-246.
 

Secondary endpoints:

 
ORR, defined as the proportion of subjects who have BOR of CR or PR measured by RECIST 1.1 (see APPENDIX V). ORR is measured from the start date of the treatment period until date of death from any cause. Subjects who are lost to follow-up and the subjects who are alive at the date of data cutoff will be censored at the date the subject was last known alive.
 
PFS, defined as the time from the first study dose date to the date of first
 

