	The dose expansion consists of 3 cohorts. The ORRs to pembrolizumab for the patients with the 3 types of cancer, who were relapsed/refractory R/R to previous chemotherapies, were 21.1% and 22,7% for urothelial cancer and gastric/GEJ adenocarcinoma, respectively. The ORR for patients with advanced NSCLC who have previously been treated with anti-PD-1/PD-L1 therapy is expected to be negligible

(i.e. <= 20%). As such, the expected response rate to the combination therapy across indications is 20% to 30%. In order to increase the estimate precision, at least 20 evaluable patients will be included in each of the 3 cohorts.
Analysis Populations
Safety population: Subjects will be evaluable for safety if they receive at least one dose of APR-246. The safety population will be used to summarize exposure and safety parameters.
DLT-evaluable population: In the safety lead-in portion of the study, subjects who either experience a DLT during first the 3 weeks (Cycle 1) of the study treatment or receive $\geq$ 75% of scheduled Cycle 1 dose of APR-246 in combination with pembrolizumab and do not experience a DLT. Any individual subject who is not evaluable for DLT will be replaced by a new subject through additional subject enrollment.
Efficacy evaluable (EE) population: All subjects who complete at least one treatment cycle of APR-246 in combination with pembrolizumab and who have at least one post-treatment clinical response assessment. Subjects who fail to complete one treatment cycle will also be considered EE if they show clear evidence of clinically significant disease progression. The EE population will be the secondary analysis population for efficacy.
PK population: Subjects will be evaluable for PK if at least one post-dose sample for PK evaluation has been obtained.
PK/Pharmacodynamic population: All the subjects who receive at least 1 dose of study drug (APR-246 pembrolizumab) and have evaluable pharmacodynamic and concentration data.
Statistical analysis
All the statistical analysis will be detailed in the statistical analysis plan.

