### 4.0 TRIAL DESIGN

### 4.1 Overview of Trial Design

This is a phase 1/2, open-label, study to determine the safety and preliminary efficacy of APR-246 in combination with pembrolizumab in subjects with solid tumor malignancies.

In the safety lead-in part of study (phase 1), the safety and the RP2D of APR-246 will be investigated. The RP2D of APR-246 will be defined as the dose at which < 2 out of 6 subjects experience DLT during the 3-week safety assessment period after the start of APR-246 administration in combination with pembrolizumab using dose de-escalation of APR-246.

In the expansion part of the study (phase 2), both safety and efficacy for the combination therapy will be investigated in the 3 cohorts.

Study treatment may be administered on an outpatient basis. No investigational or commercial anti-tumor agents or therapies other than those described below may be administered with the intent to treat the patient's underlying malignancy.

The study will include a safety lead-in dose-finding portion followed by expansion portion. During the safety lead-in portion of the study, subjects with (non-CNS primary) solid tumor malignancies will receive pembrolizumab in combination with APR-246 in a 3 + 3 dose deescalation design.

Dosing will begin at the full dose of both drugs due to the well-established safety profiles of APR-246 and pembrolizumab, the non-overlapping mechanisms of action, and the intent to treat patients at doses shown to be effective in previous studies. Lower dose levels of APR-246 will be explored as necessary depending on observed AEs.

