# 6.1.2 Recommended Phase 2 Dose (RP2D)

The RP2D of APR-246 will be defined as the dose at which < 2 out of 6 subjects experience DLT during the 3-week safety assessment period after administration of APR-246 in combination with pembrolizumab.

A DRT consisting of the Medical Monitor, Site Principal Investigators, and other clinical research personnel that the Sponsor may deem appropriate, will hold Data Review Meetings (DRM) on an interim basis at a frequency dependent upon study accrual. At these meetings, the DRT will review AEs and DLTs and make recommendations regarding the RP2D. In the expansion portion of the study, the DRT will evaluate safety and tolerability after 5 subjects have completed 1 cycle of treatment in each cohort. All accumulated safety data will be discussed during DRMs.

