# 9.2 Analysis Populations

*Safety population*: Subjects will be evaluable for safety if they receive at least one dose of APR-246. The safety population will be used to summarize exposure and safety parameters.

*DLT-evaluable population*: All subjects who either experience a DLT during first the 3 weeks (Cycle 1) of the study treatment or receive  $\geq$  75 % of scheduled Cycle 1 dose of APR-246 in combination with pembrolizumab and do not experience a DLT. Any individual subject who is not evaluable for DLT will be replaced by a new subject through additional subject enrollment.

*Efficacy evaluable (EE) population*: All subjects who complete at least one treatment cycle of APR-246 in combination with pembrolizumab and who have at least one post-treatment clinical response assessment. Subjects who fail to complete one treatment cycle will also be considered EE if they show clear evidence of clinically significant disease progression. The EE population will be the secondary analysis population for efficacy.

*PK population*: Subjects will be evaluable for PK if at least one post-dose sample for PK evaluation has been obtained.

*PK/Pharmacodynamic population:* All subjects who receive at least 1 dose of study drug (APR-246 pembrolizumab) and have evaluable pharmacodynamic and concentration data.

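### Two of the DLT criteria in Section 6.1.1 can be met after Day 21, but the RP2D counts only DLTs in the first 3 weeks and nothing says how a late-met DLT is dated

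*Combined protocol and SAP*

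**What the plan says.** Section 6.1.1 defines a DLT as any one of four things. The first two are tied to the 3-week period or to Cycle 1: a listed toxicity, or failure to give at least 75% of the planned APR-246 because of toxicity. The third is discontinuation for treatment-related toxicity, with no time limit. The fourth is a "Greater than 4-week delay in starting Cycle 2 because of a treatment-related toxicity, even if the toxicity does not meet DLT criteria".

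The RP2D is narrower. Section 6.1.2 sets it at the dose where fewer than 2 of 6 "subjects experience DLT during the 3-week safety assessment period after administration of APR-246 in combination with pembrolizumab". The synopsis and Section 4.1 use the same window. Section 4.1 assesses each cohort once its last enrolled subject has finished the 3 weeks.

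For the DLT-evaluable population, Section 9.2 takes "All subjects who either experience a DLT during first the 3 weeks (Cycle 1) of the study treatment or receive" at least 75% of the "scheduled Cycle 1 dose of APR-246 in combination with pembrolizumab and do not experience a DLT". It adds: "Any individual subject who is not evaluable for DLT will be replaced by a new subject through additional subject enrollment". The synopsis repeats this population. The synopsis also has an MTD Analysis Set, which keeps every lead-in subject who completes Cycle 1.

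The text after the DLT table in Section 6.1.1 says that AEs meeting the criteria but occurring after the evaluation period are not DLTs. It replaces only subjects who stop before completing Cycle 1 for a reason other than a DLT.

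**The concern.** The delay criterion exists to catch toxicities that the DLT table misses; its own wording says so. The rule that sets the dose looks only at a window in which that criterion cannot be met, and it may be applied before the outcome is known. The discontinuation criterion has the same problem whenever the stop falls after Day 21.

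DLT occurrence and the RP2D are both primary endpoints, and up to 100 expansion subjects are to be treated at the chosen dose. A DLT left out of the count can only make a dose look safer, so the error runs towards the higher dose.

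**Working it through.** **The plan's own figure.** Three dose levels × 6 subjects = 18, which matches the stated maximum of 18 DLT-evaluable lead-in subjects. The plan gives no calendar day for the delay criterion, so it is derived here.

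**When the delay criterion is met.** Cycles are 21 days (Section 6.1).
- Cycle 2 is due on Day 1 + 21 = Day 22.
- A delay of exactly 4 weeks is Day 22 + 28 = Day 50, so more than 4 weeks is first met on Day 51.
- The window closes on Day 21, and 51 − 21 = 30 days.
- Counting from either end of a ±3-day Cycle 2 visit window gives Day 48 or Day 54. No choice falls within 3 weeks.

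**When the discontinuation criterion is met.** This can be inside or outside the window. One route outside is the Section 6.2 rule that stops treatment for an unresolved TEAE. Read as a full 3 weeks, the earliest stop is Day 1 + 21 = Day 22. An onset on Day 21 gives Day 42; a clock starting with the hold on Day 22 gives Day 43.

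**Three readings of one subject** (full Cycle 1 dosing, toxicity beginning in Cycle 1, late criterion met afterwards):

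| Reading | Status | Effect on RP2D count |
|---|---|---|
| Not a DLT, because met after the window | Evaluable non-DLT | Event lost |
| A DLT, but not in the first 3 weeks (literal Section 9.2) | Fails both arms of the definition; replaced | Event and subject lost |
| A DLT dated by toxicity onset | Counted DLT | Counted, but may be known too late |

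The second reading conflicts with the MTD Analysis Set, which keeps the same subject. On the third, timing depends on enrolment order. A subject who started d days before the last one reaches Day 51 on the last subject's Day 51 − d. That is Day 21 or earlier only if d is at least 30.

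**Effect at the decision boundary** (one in-window DLT, one late DLT):

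| Subjects | Late DLT counted | Kept as non-DLT | Excluded and replaced |
|---|---|---|---|
| 6 | 2/6: go to next lower dose | 1/6: RP2D declared | 1/5, replacement decides |
| 3 | 2/3: go to next lower dose | 1/3: enroll 3 more | 1/2, replacement needed |

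**Illustration with assumed rates.** The documents give no DLT rates. Let pe be the in-window DLT probability and pl the probability of a late DLT with no in-window DLT. A dose is declared the RP2D if X ≤ 1 of 6, with probability (1 − p)^6 + 6p(1 − p)^5. Take pe = 0.20 and pl = 0.10:
- counted, p = pe + pl = 0.30: 0.420
- kept as non-DLT, p = pe = 0.20: 0.655
- excluded and replaced, p = pe/(1 − pl) = 0.20/0.90 = 0.222: 0.601

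Over pe 0.10 to 0.30 and pl 0.05 to 0.15, not counting late DLTs raises the probability by 0.10 to 0.35 (kept) or 0.07 to 0.32 (replaced).

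**The case against.** A reader might infer from Section 9.2 that the affected subject would certainly be excluded and replaced. The documents do not support that. Exclusion needs the DLT to be dated late for the first arm, and the no-DLT condition in the second arm to have no time limit. Consistent onset dating makes the subject a counted DLT. Consistent dating by completion arguably makes the event a non-DLT under the closing text of Section 6.1.1, and the subject stays evaluable. What stands is that the plan does not choose.

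A reader might also infer that toxicity discontinuations fall on Day 22 at the earliest. That holds only for stops under the Section 6.2 rule read as a full 3 weeks. Grade 4 CNS events or confirmed QTc prolongation with other causes excluded can end treatment inside the window.

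The Section 6.2 rule may also stop a subject by Day 42 or 43, before a delay reaches Day 51. Where it does, the problem passes to the discontinuation criterion, which is still met outside the window.

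The affected set is small. Most related Grade 3 non-hematologic toxicity lasting more than 3 days is already a DLT. What remains is mainly prolonged toxicity below the table thresholds, such as Grade 3 neutropenia or low platelets without bleeding or transfusion.

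Finally, the Data Review Team sees AEs as well as DLTs and reviews safety again after 5 subjects in each expansion cohort. So it would be too strong to say that a late event can never influence the dose. But that is discretion; the written count does not include the event.

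**Conclusion.** The concern holds as an unresolved conflict between the DLT definition and the rule that uses it. On the day count alone, the delay criterion cannot be met in the window that drives the RP2D. Two of the three available readings drop the event, both in favour of the higher dose. The third counts it but lets the decision come up to 30 days before it is known.

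The size is one subject at the boundary between 1 of 6 and 2 of 6, which is enough to change the dose carried into expansion. The day count rests on the 21-day cycle and the boundary example on the stated decision rule. The probabilities rest on assumed rates and show direction and possible scale only. Because few subjects can be affected, this is a wording defect worth correcting before the lead-in rather than a failure of the design.

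**What to change.** 1. In Section 9.2, the synopsis, Section 4.1 and Section 6.1.2, count any DLT defined in Section 6.1.1 that arises from a toxicity beginning in the first 3 weeks (Cycle 1), whenever the delay or discontinuation criterion is met.
2. In Section 4.1, treat a subject whose Cycle 2 is on hold for treatment-related toxicity as pending until Cycle 2 starts, treatment is discontinued, or the delay passes 4 weeks. Hold the dose decision only if that subject could change it. With one in-window DLT and one pending subject among 6, wait. With no DLT and one pending, or with two DLTs already, do not.

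Do not add a statement that the 3-week TEAE rule in Section 6.2 takes precedence over the 4-week limit. It would end most holds by Day 42 or 43 and largely empty the delay criterion that the change is meant to keep.

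The cost is wording in four places and an occasional wait of up to about 30 days (Day 51 instead of Day 21). The planned sample size does not change.

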# 6.1.2 Recommended Phase 2 Dose (RP2D)

The RP2D of APR-246 will be defined as the dose at which < 2 out of 6 subjects experience DLT during the 3-week safety assessment period after administration of APR-246 in combination with pembrolizumab.

A DRT consisting of the Medical Monitor, Site Principal Investigators, and other clinical research personnel that the Sponsor may deem appropriate, will hold Data Review Meetings (DRM) on an interim basis at a frequency dependent upon study accrual. At these meetings, the DRT will review AEs and DLTs and make recommendations regarding the RP2D. In the expansion portion of the study, the DRT will evaluate safety and tolerability after 5 subjects have completed 1 cycle of treatment in each cohort. All accumulated safety data will be discussed during DRMs.

